2.6.9 Association of ADA with PK

The following analysis will be considered: 1. Within Subject level AUC change from baseline to end of the double-blind treatment period will be plotted by peak titer category. Gender will be separated by different color. 2. Between subject comparison of ADA-positive vs. ADA negative. Plot of AUC at baseline compared to timepoints where full PK assessment is available. Patients will be evaluated by titer categories based on titer category at the time of PK assessment. Patients will be separated based on treatment groups. 3. Summary table to include AUC and % change from Day 1 at each scheduled visit by peak titer categories. 4. Data will be assessed for switch patients as appropriate.

2.6.10 Association of ADA and PD marker

Hex-4 is a clinically relevant PD marker that is related to the drug's mechanism of action. Summary table of number (%) of patients with elevated urinary hex-4 by titer value at the specified visit (eg, peak titer categories) over time will be provided. Within-subject changes from baseline in PD marker will be evaluated with respect to the changes in the status and/or titer value of ADA/NAb (neutralizing antibodies).

2.6.11 Association of ADA with selected efficacy

Correlation analysis will be performed between immunogenicity (ADA titers, response categories and neutralizing ADA) and FVC, 6MWT, (raw and percent predicted), MIP, MEP.

2.7 SUMMARY OF PHARMACOKINETIC DATA

Pharmacokinetic parameters will be summarized using descriptive statistics by study weeks. Plasma concentration data will be summarized using descriptive statistics by treatment weeks. The population pharmacokinetic results will be documented in a separate report.

2.8 ANALYSES OF PHARMACODYNAMICS ENDPOINT DATA

Creatinine-normalized urine Hex4 levels will be summarized using descriptive statistics at each scheduled study visit. Observed measurements as well as the change from baseline will be summarized. If a linear trend in the change of urine Hex4 levels is observed, a longitudinal model may be employed to model change from baseline over time. In addition, 95% confidence intervals of changes will be presented.

Correlation between PK endpoints and urine Hex4 levels will be explored as appropriate.

Similar analyses will be carried out to explore the relationship between other PD endpoints, biomarkers, efficacy assessments, and exploratory endpoints.

2.9 ANALYSES OF QUALITY OF LIFE/HEALTH ECONOMICS VARIABLES

The 18 questions for the R-PAct will be scored according to the 0 (unable to perform) to 2 (able to perform without difficulty) Likert scale and will have a descriptive analysis by treatment group.

Scores for the PDSS and PDIS will be calculated separately for each questionnaire, as well as a composite score for both questionnaires together. Note that these are exploratory endpoints recently developed, and the scoring method for these scales is still under development. These will be finalized prior to study unblinding and described in a separate document.

2.10 DATA HANDLING CONVENTIONS

2.10.1 General conventions

In general, the baseline value is defined as latest value prior to the start of first infusion in PAP or ETP. In the case an assessment performed on the same date as the first infusion date, but it is impossible to determine the evaluation time relative to first infusion start time, the evaluation time will be assumed to be following the protocol-defined schedule.

2.10.2 Data handling conventions for primary and secondary efficacy variables

The baseline value for the efficacy variables is the last non-missing measurement prior to the first infusion of the study drug. The ETP baseline value for the efficacy variables is the last non-missing measurement prior to the first infusion of avalsuglucosidase alfa in ETP.

If the baseline value is missing, the patient will be excluded from the MMRM efficacy analyses under MAR assumption. The missing data handling for the key efficacy endpoints are described in [Section 2.1.3](#).

2.10.3 Missing data handling in data presentation

In general, missing baselines will not be imputed. The following approaches are default methods for missing data handling in summary tables.

- Categorical data at baseline will be summarized for each treatment group using counts (n) and percentages (%). Denominator will be the analysis population specified for the summary, unless otherwise specified. Missing data may be presented as a separate category.
- Continuous data: The analyses and summaries for variables with continuous scales will be based on observed data only.

Handling of computation of treatment duration if investigational medicinal product end of treatment date is missing

For the calculation of the treatment duration, the date of the last dose of IMP is equal to the date of last administration reported on drug exposure case report form page. If all the infusion dates are missing, then the duration is missing.

The last dose intake should be clearly identified in the case report form and should not be approximated by the last returned package date.

Handling of missing/partial dates for adverse events or concomitant medications

Missing or partial adverse event onset dates and times will be imputed so that if the partial adverse event onset date/time information does not indicate that the adverse event started prior to treatment or after the treatment-emergent adverse event period, the adverse event will be classified as treatment-emergent. No imputation of adverse event end dates/times will be

performed. These data imputations are for categorization purpose only and will not be used in listings. No imputation is planned for date/time of adverse event resolution.

No imputation for medication start/end dates or times will be performed. If a medication date or time is missing or partially missing and it cannot be determined whether it was taken prior or concomitantly, it will be considered a prior, concomitant, and post-treatment medication.

Handling of missing or partial birth date for calculation of age

Complete missing of birth date is not expected for the study. However, there could be rare situations in which the birth day or month is not provided for the subject due to confidentiality. In this case, the missing day will be imputed as 15th of the month, and missing month will be imputed as June as default. The adjustment maybe needed in the case of conflicting with study dates. These adjustments should be very rare and will be documented in the data specification document.

Handling of adverse events when date and time of first investigational medicinal product administration is missing

When the date and time of the first IMP administration is missing, all adverse events that occurred on or after the day of randomization should be considered as treatment-emergent adverse events. The exposure duration should be kept as missing.

The last dose intake should be clearly identified in the case report form and should not be approximated by the last returned package date.

Handling of missing assessment of relationship of adverse events to investigational medicinal product

If the assessment of the relationship to IMP is missing, then the relationship to IMP in the frequency tables is considered as possibly related, but no imputation should be done at the data level.

Handling of missing severity of adverse events

If the severity is missing for 1 of the treatment-emergent occurrences of an adverse event, the maximal severity on the remaining occurrences will be considered. If the severity is missing for all the occurrences, a “missing” category will be added in the summary table.

Handling of potentially clinically significant abnormalities

If a patient has a missing baseline he will be grouped in the category “normal/missing at baseline.”

For PCSAs with 2 conditions, one based on a change from baseline value or a normal range and the other on a threshold value, with the first condition being missing, the PCSA will be based only on the second condition.

For a PCSA defined on a threshold and/or a normal range, this PCSA will be derived using this threshold if the normal range is missing; eg, for eosinophils the PCSA is >0.5 GIGA/L or $>$ ULN if $ULN \geq 0.5$ GIGA/L. When ULN is missing, the value 0.5 should be used.

Measurements flagged as invalid by the laboratory will not be summarized or taken into account in the computation of PCSA values.

Handling of ADA titer with missing or non-numerical values

If the ADA titer is reported as “< value”, then the actual value is imputed as this value. For example, “<100” will be imputed as 100. A negative ADA status will be assumed as a value of 0 (will be excluded when geometric mean of the group needs to be calculated).

2.10.4 Study day calculation

Based on study protocol, study Day 1 is the date of first study infusion.

Study day for a given assessment is defined as the assessment date - date of first study infusion + 1 if the assessment date is on or after Day 1, or assessment date - date of first study infusion if the assessment date is before Day 1.

If a randomized patient is not treated (first infusion date is missing), study Day 1 is the date of randomization.

2.10.5 Windows for time points

The visit windows for efficacy endpoints specified in [Table 16](#) are defined in following table. For analysis purpose, a larger window (as shown in the last column of [Table 14](#)) will be used. This will be applicable for those analyses requiring visit information.

Table 14 - Study visit nominal visit days and windows for efficacy endpoints

Scheduled Visit	Visit window defined in protocol in study days	Visit window for analysis purpose in study days
Screening/Baseline	Day -14 to -1	(-28, the day before 1st infusion)
Week 13	Day 85 ±14	(the day after 1st infusion, Day 85 +41)
Week 25	Day 169 ±14	Day 169 (-42, +41)
Week 37	Day 253 ±14	Day 253 (-42, +41)
Week 49	Day 337 ±14	(Day 337 -42, the day prior to the 1st ETP treatment or Day 337 + 41 if 1st ETP treatment is missing)
Week 61	Day 421 ±14	(the day after the 1st ETP treatment, Day 421 +41)
Week 73	Day 505 ±14	Day 505 (- 42, +83)
Week 97	Day 673 ±14	Day 673 (-84, +83)
Week 121	Day 841 ±14	Day 841 (-84, +83)

Scheduled Visit	Visit window defined in protocol in study days	Visit window for analysis purpose in study days
Week 145	Day 1009 ±14	Day 1009 (-84, +83)
Week 169	Day 1177 ±14	Day 1177 (-84, +83)
Week 193	Day 1345 ±14	Day 1345 (-84, +83)
Week 217	Day 1513 ±14	Day 1513 (-84, +83)
Week 241	Day 1681 ±14	Day 1681 (-84, +83)
Week 265	Day 1849 ±14	Day 1849 (-84, +83)

The analysis visit will be defined by comparing the actual visit date with the nominal (or target) date and the corresponding analysis window from [Table 14](#) . If more than one non-missing values are assigned to the same visit, then the one closest to the target date will be used in the by-visit analysis. Multiple values on the same date will be averaged first. If two assessments are on different date but equal distance from the target date, the later date will be used.

For the safety analyses (laboratory, ECG and vital signs), the nominal visit will be used for the by-visit type of analyses.

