2.1.4 Safety endpoints

The safety analysis will be based on the reported adverse events and other safety information, such as clinical laboratory data, vital signs, ECG, physical examination, weight, height, and immunogenicity.

Observation period

The observation period will be divided into the following epochs:

- The pre-treatment epoch is defined as the time from the signed informed consent date up to first administration of IMP.
- The treatment epoch for PAP is defined as the time from the first administration of the study drug to,
 - The time just prior to the first administration of the study drug in ETP, or,
 - Up to four weeks (28 days) after the last infusion date if the patient does not go to ETP. If the patient enrolls in another study or receives commercially available ERT, the follow-up period may be reduced from 4 to 2 weeks.
- The treatment epoch for ETP is defined as the time from the first administration of the study drug in ETP to the last administration of the study drug + up to 4 weeks (28 days). If the patient enrolls in another study or receives commercially available ERT, the follow-up period may be reduced from 4 to 2 weeks.
- The post treatment epoch for PAP is defined as the time beyond the treatment epoch in PAP through the last study assessment; this epoch is defined only for patients who do not receive any infusion in ETP.
- The post treatment epoch for ETP is defined as the time beyond the treatment epoch in ETP through the last study assessment, defined only for patients who receive any infusion in ETP.

The on-study observation period is pre-treatment, treatment and post treatment epoch.

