2.5 ANALYSES OF EFFICACY ENDPOINTS

All efficacy endpoints will be summarized descriptively at each study visit, as well as the last observation available during the PAP. All efficacy analyses will be performed based on the mITT

population. Corresponding analysis will be performed for PP population for the primary efficacy endpoint. If the pure ITT (all randomized patients) population is different from the mITT population, we plan to perform a sensitivity analysis in this population as well to assess the robustness of the results.

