
The primary statistical objective is to test the non-inferiority of avalglucosidase alfa versus alglucosidase alfa at two-sided 5% level of significance. The null and alternative hypotheses based on a non-inferiority margin of 1.1 are described as H_{01} and H_{a1} below:

H_{01} : avalglucosidase alfa–alglucosidase alfa \leq -1.1 versus H_{a1} : avalglucosidase alfa–alglucosidase alfa $>$ -1.1

If the lower bound of the two-sided 95% confidence interval for the difference of avalglucosidase alfa-alglucosidase alfa is larger than -1.1, the study will be considered to have met its primary objective and the non-inferiority of avalglucosidase alfa over alglucosidase alfa is established.

After non-inferiority is demonstrated, a test for superiority of avalglucosidase alfa versus alglucosidase alfa will be performed with an overall two-sided 5% level of significance.

The following SAS code will be used for the primary efficacy analysis:

```
ods output Diff = out1
      LSMMeans = out2;
proc mixed data = DATAIN method = reml;
  class TRT VISIT SEX USUBJID;
  model CHG_FVC = BL_FVC SEX AGE TRT VISIT TRT*VISIT/ ddfm = kr;
  repeated VISIT/type = un subject = USUBJID r;
  lsmeans TRT TRT*VISIT/cl diff;
run;
```

where TRT = treatment group, VISIT = (week 13, 25, 37, 49), SEX = (male, female), AGE = age at baseline (continuous), USUBJID = unique patient ID, CHG_FVC is the change from baseline in FVC (% predicted), and BL_FVC is the baseline FVC (% predicted) value.

The same analysis as described above will be performed for the PP population to assess the robustness of the study outcome.

A US FDA-specific exploratory analysis will be conducted using the method described above for those patients in the mITT population 8 years of age or older in order to match the lower age range of patients in the LOTS trial of alglucosidase alfa. This analysis will be used to support US approval.

In the case that both NI and superiority of FVC (% predicted) are demonstrated, a superiority test for 6MWT will be performed with a two-sided alpha of 0.05.

Note that the type I error is controlled for the primary endpoint of FVC (% predicted) in the above testing procedure. Analyses of secondary efficacy endpoints in PAP

The secondary efficacy endpoints for PAP are described in [Section 2.1.3.2](#).

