2.5.3.2 Sensitivity analyses with alternative model or different distribution assumption

The following analyses will be performed to address potential deviation from the primary model assumption

1. An analysis of covariance including baseline FVC, age, gender, treatment group as covariates will be performed for the endpoint of change from baseline in FVC % predicted at Week 49. For the patients who are known to start alternative treatment prior to Week 49, the last value prior to initiation of an alternative treatment will be used in the analysis. For other patients who prematurely discontinued prior to Week 49 but with unknown alternative treatment information, their last value prior to dropout will be used in the analysis.
2. A Wilcoxon-Mann-Whitney (WMW) will be performed for change from baseline in FVC (% predicted) at Week 49. Missing FVC (% predicted) at Week 49 will be imputed by baseline or last assessment (within PAP) for the subject, whichever is worse. This analysis will assess the robustness of the results when the normality assumption which underlies the MMRM model is deviated.
3. Change from baseline in FVC (% predicted) will be analyzed with MMRM model including the covariates specified in the primary model (baseline FVC, age, gender, treatment group, visit, and treatment-by-visit interaction as fixed effects).

4. The FVC (% predicted) will be analyzed with a Linear Mixed Effects model which includes fixed effects of age (as continuous variables), gender, treatment, time (in years) and the treatment * time interaction; as well as subject specific random intercept and random slope. The model will be fitted using restricted maximum likelihood estimation with the PROC MIXED procedure in SAS. Comparison between treatment groups will be made by testing and estimating the contrast of the treatment * time interaction in the model. All FVC (% predicted) values from baseline through Week 49 (based on actual assessment date) will be included for this analysis. This analysis model will be appropriate if the FVC (% predicted) over time is approximately linear.

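### SAP Table 14 gives the day of the first open-label infusion to no efficacy visit, so a Week 49 test made up that morning is lost from the by-visit Week 49 analyses

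*SAP*

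**What the plan says.** SAP 2.10.5 sets the rule for efficacy data: "The analysis visit will be defined by comparing the actual visit date with the nominal (or target) date" and with the Table 14 analysis window. Nominal visits are kept for safety data only.

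The two relevant rows of Table 14 are:

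- Week 49: "Day 337 -42, the day prior to the 1st ETP treatment or Day 337 + 41 if 1st ETP treatment is missing"
- Week 61: "the day after the 1st ETP treatment, Day 421 +41"

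The primary MMRM in SAP 2.5.1 uses "VISIT = (week 13, 25, 37, 49").

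Other sections treat data up to the moment of the first ETP infusion as belonging to the blinded period:

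- SAP 2.1.4 runs the blinded treatment epoch to "The time just prior to the first administration of the study drug in ETP".
- SAP 2.1.3 and 2.10.2 define ETP baseline as the last value before that infusion, with no calendar-day cut. SAP 2.5.5 equates ETP baseline with Week 49.
- SAP 2.10.1 says that an untimed assessment on the date of first infusion is taken to have followed the protocol order.

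Protocol 9.1.1 and 9.2.1.1 place PFT and 6MWT before infusion. Protocol 9.1.1 allows a missed or failed PFT to be made up within 45 days. Protocol 10.1.8 keeps efficacy tests from a missed visit attached to that visit, even when they are done outside its window.

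**The concern.** One window ends the day before the first ETP infusion and the next starts the day after, so an efficacy test dated on the infusion day has no analysis visit. The value is valid: it is taken before any open-label drug is given and is the last on-blind measurement.

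If it is the patient's only value from Day 295 onward:

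- Week 49 is missing in the primary MMRM, and in the secondary MMRMs for tests made up the same day.
- The patient counts as a non-responder for FVC (SAP 2.5.3.4.1), and for 6MWT (SAP 2.5.1.1.2) if that test was also made up that day.
- On a strict reading the patient fails the per-protocol requirement of a valid Week 49 FVC (SAP 2.3.1.2).
- On the same reading, a comparator patient has no observed Week 49 value in the Week 49 to Week 97 switch analysis (SAP 2.5.5.2).

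This also conflicts with the treatment-policy estimand in SAP 1.2.1, which is meant to use all observed data.

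A separate gap in the same table is that its last row is Week 265. Protocol 10.1.5.4 schedules PFT and 6MWT at Week 289, the SAP itself plans 144 extra weeks (SAP 1.1), and Table 16 has an end-of-treatment column.

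**Working it through.** **Target days.** Day = (week − 1) × 7 + 1. This reproduces all 14 post-baseline target days in Table 14, for example Week 49 = 48 × 7 + 1 = 337 and Week 265 = 264 × 7 + 1 = 1849. The same formula gives Week 51 = 351 and Week 289 = 2017.

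**Windows around the switch.** The first ETP infusion is at V28/Week 51, ±7 days (protocol 8.1).

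| Item | Calculation | Days |
|---|---|---|
| Protocol Week 49 window | 337 ± 14 | 323–351 |
| First ETP infusion | 351 ± 7 | 344–358 |
| SAP Week 49 window, infusion on Day 351 | 337 − 42 to 351 − 1 | 295–350 |
| SAP Week 49 window, no ETP infusion | 337 − 42 to 337 + 41 | 295–378 |
| SAP Week 61 window, infusion on Day 351 | 351 + 1 to 421 + 41 | 352–462 |
| Latest make-up for a PFT due on Day 337 | 337 + 45 | 382 |

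On the nominal schedule Day 351 is unassigned, yet it is the last day of the protocol's own Week 49 window. With the infusion window, the first ETP infusion day can fall inside the protocol's Week 49 window on any of Days 344–351.

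**All joins in Table 14.** Reading the windows as closed intervals, there are 14 joins between successive rows. Twelve are contiguous: 126/127, 210/211, 294/295, 462/463, 588/589, 756/757, 924/925, 1092/1093, 1260/1261, 1428/1429, 1596/1597 and 1764/1765. The two exceptions are Day 1 and the first ETP infusion day. A day-by-day check of Days 2–1092, with the first ETP infusion moved from Day 296 to Day 462, left exactly one unassigned day each time: the infusion day. Open intervals leave more gaps and still omit that day.

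The Day 1 gap arises in the same way, because the Week 13 window is "the day after 1st infusion, Day 85 +41". It does no harm, since baseline has its own definition. No such rule recovers Week 49: the same-day convention in SAP 2.10.1 concerns baseline, and SAP 2.10.6 covers only laboratory, vital-sign and ECG data.

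**Who can be affected.** A test done as scheduled at V27 precedes the V27 infusion, and infusions must be at least 7 days apart (protocol 8.1), so it cannot fall on the ETP infusion day. Only a missed, failed or postponed test can. V28 is the next scheduled site visit after V27.

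**Size of one loss.** 96/2 = 48 per arm, and 1/48 = 2.1%. With 10% missing, 96 × 0.9 = 86.4, or about 43 per arm. As a check on this basis, a noncentral t calculation with 43 per arm, SD 5.1 and a distance of 2.0 + 1.1 = 3.1 gives 79.6% power, matching SAP Table 4. Then:

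- SE with 43 and 43: 5.1 × √(2/43) = 1.100
- SE with 42 and 43: 5.1 × √(1/42 + 1/43) = 1.106
- Ratio 1.006, a rise of 0.6%, and less in the MMRM, which keeps the patient's earlier visits

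**End of the table.** Week 265 ends at 1849 + 83 = Day 1932. Week 289 is Day 2017, which is in no window.

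**The case against.** The strongest counter-argument is protocol 10.1.8. A make-up test stays attached to the visit that was missed, so a Week 49 test done at V28 is recorded as Week 49, and one could say that it keeps that label in the analysis. It does not: SAP 2.10.5 re-windows efficacy data by actual date and keeps nominal visits for safety only. The protocol rule therefore makes the conflict plainer and does not resolve it.

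Several limits do stand:

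- The trigger needs three things at once: no valid V27 test, no other value from Day 295, and a make-up on exactly the first ETP infusion day. The protocol asks for make-ups promptly, and any earlier date is captured.
- Some analyses could still use the value. These are the summary of each endpoint "as well as the last observation available during the PAP" (SAP 2.5), the linear mixed model in SAP 2.5.3.2 item 4 ("All FVC (% predicted) values from baseline through Week 49 (based on actual assessment date) will be included for this analysis"), and the Wilcoxon-Mann-Whitney test in item 2, where it would count only if worse than baseline.
- The per-protocol criterion does not cite Table 14, and SAP 2.5.5 could be read as supplying the Week 49 value for the switch analysis.
- The 45-day make-up rule is for PFT only. For 6MWT the route is the missed-visit rule in protocol 10.1.8. SF-12 need precede infusion only where possible, so the timing argument is weaker there.
- The Week 289 omission affects descriptive data only, and the last-observation summary would still report those values.

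**Conclusion.** The point holds and is minor. As written, Table 14 drops a valid pre-infusion Week 49 value from the by-visit analyses, including the primary MMRM, while other SAP sections treat the same value as Week 49 data. The conclusion rests on the windows being closed intervals, on assignment by actual date, and on the protocol order of testing before infusion. The documents do not say how many patients would be affected, and the number is likely very small. Each one costs 2.1% of a planned arm and about 0.6% on the standard error on the t-test basis. No bias is claimed, and no change to the non-inferiority conclusion is shown. The missing Week 289 row is a separate, descriptive matter.

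**What to change.** In Table 14, end the Week 49 window at the start of the first ETP infusion, counting same-day pre-infusion values (Day 378 if there is no ETP infusion), and start Week 61 after that infusion. Add one sentence extending the SAP 2.10.1 convention to this day, so that a same-day test with no recorded time is taken as pre-infusion. With this change every day from 2 to 1092 has a visit and none has two.

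Separately, add a Week 289 row, Day 2017 (−84, +83). That is Days 2017 − 84 = 1933 to 2017 + 83 = 2100, which joins the Week 265 window ending on Day 1932.

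The cost is two cell edits, one new row and one sentence, with no new procedures or data. If the analysis has already been run, a single query for efficacy tests dated on the first ETP infusion day would show whether anyone was affected, and the result can be documented.
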